3.1. Hypothesis

The Test product, a topical transdermal glucosamine cream (TGC® Transdermal Glucosamine Cream Plus Capsaicin, Lynk Biotechnologies Pte Ltd) is able to deliver glucosamine, through the skin, to the synovial fluid of osteoarthritic (OA) joints.

3.2. Objective

To assess the bioavailability of the Test product: a topical transdermal glucosamine cream (TGC® Transdermal Glucosamine Cream Plus Capsaicin, Lynk Biotechnologies Pte Ltd containing 10% w/w Glucosamine Sulphate.2KCl presented as a finished product) in the synovial fluid of OA joints.

3.3. Purpose / Importance of the research

Glucosamine is commonly administered orally to human patients in the form of tablets or capsules with a recommended dosage of 20mg/kg/day^[7]. As some patients are not able to swallow these solid dosages, and due to the potential issues in drug absorption in the gastro-intestinal tract and in the first-pass effect of the liver^[7, 10], this transdermal drug delivery technology can offer an alternative route to deliver glucosamine.

Another advantage of this technology is that it offers a targeted approach; glucosamine can be delivered to the area where it is the most needed for the patient. Lastly the study will allow us to establish a baseline for the endogenous glucosamine concentration in the synovial fluid of diseased knee in OA joints.

4. **Trial design**

- 4.1. A specific statement of the primary endpoints and the secondary endpoints, if any, to be measured during the trial.

4.1.1. Primary endpoints

To show that the level of glucosamine in synovial fluid has statistically increased after the Test product topical application.

[figure not shown]
4.1.2. Secondary endpoints

To determine the endogeneous level of glucosamine in synovial fluid and establish a baseline for OA joints.

4.2. Trial design

This is an open label, single dose design to examine the glucosamine content in the synovial fluid after applying the Test product on OA patient's knee.

4.3. Procedure flowchart:

4.4. A description of the measures taken to minimise / avoid bias, including randomisation / blinding:

The analytical results are objective. There is no possibility of subjective bias or placebo effect. Therefore there is no measure necessary and hence no randomization needed.

As for the selection of subjects, there is no need to have measures to minimise bias. There is no bias since we take all patients that come in to the clinic for treatment. Patients are not selected for control or test group, they select themselves by choosing (yes or no) to apply the Test product.

- 4.5. A description of the trial treatment(s) and the dosage and dosage regimen of the investigational product(s). This also includes description of the dosage form, packaging, and labelling of the investigational product(s).

A single dose of 2g of the Test product will be applied topically on the affected knee of the Test Group subjects. The Test product is presented in a white tub, labelled with the product name, Batch Number and Expiry date.

- 4.6. The expected duration of subject participation, and a description of the sequence and duration of all trial periods, including follow-up, if any.

Single session, up to 4 hours, for the cream application and joint's fluid aspiration. The tapping of synovial fluid should be done between 1 and 3 hours following cream application (for the Test group). No follow-up needed.

- 4.7. A description of the "stopping rules" or "discontinuation criteria" for individual subjects, parts of trial and entire trial.

Subjects participation may be terminated if:

- Allergy occurs after cream application and before tapping of synovial fluid
- Non-compliance to any of the exclusion/inclusion criteria

Subjects are free to withdraw at any time, without giving a reason. This will not affect the standard of care they receive.

- 4.8. Accountability procedures for the investigational product(s), including the placebo(s) and comparator(s), if any.

There is no risk of any mix up since there is no comparator or placebo arm in this study.

- 4.9. Maintenance of trial treatment randomisation codes and procedures for breaking codes.

The subjects will be identified via subject ID, a 3 digits number (e.g: 123). Samples will be labelled with the subject ID.

Personal information will be treated as confidential and accessible only to the investigators of this study.

Scientific analysis and testing will be carried out first before revelation of codes.

- 4.10. The identification of any data to be recorded directly on the CRFs (i.e. no prior written or electronic record of data), and to be considered to be source data.

To refer to the Data Record Form attached. Gender and age may be used for sub-group analysis.

5. Selection and Withdrawal of Subjects

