All serious adverse events (SAEs) that are unexpected and related to the Test product will be reported to HSA. The investigator is responsible for informing HSA no later than 15 calendar days after first knowledge that the case qualifies for expedited reporting. For fatal or life-threatening cases, HSA will be notified as soon as possible but no later than 7 calendar days after first knowledge that a case qualifies, followed by a complete report within 8 additional calendar days.

All reports will be sent to the Clinical Trial Branches (HSA), and other official parties requiring them (e.g: IRB).

The PI will take all appropriate measures to ensure the safety of the patients, including referral to a specialist if indicated.

9. **Statistics**

9.1. A description of the statistical methods to be employed, including timing of any planned interim analysis(es), and the level of significance to be used.

Statistical analysis will be performed using a one-sided Z-test, which will be used to determine if the glucosamine content in synovial fluid obtained from the Test group is significantly higher than the glucosamine content in synovial fluid obtained from the Control group. The statistical evaluation will be determined at $P < 0.01$.

9.2. The number of subjects planned to be enrolled. In multicentre trials, the numbers of enrolled subjects projected for each trial site should be specified. Reason for choice of sample size, including reflections on (or calculations of) the power of the trial and clinical justification.

A total of 240 osteoarthritic adult male and female patients (120 for the Test group, and 120 for the Control group) will be enrolled in this study. It is assumed that under single dose and with this study design the planned number of subjects is sufficient to achieve the objective of the study.

The sample sizes are sufficient to assume normality while generating a meaningful statistical comparison using the Z-test.

This trial relies on the scientific analysis of the synovial fluid collected, from patients. Therefore it eliminates patient's subjectivity and bias. Hence the trial sample size could be correspondingly reduced.

All eligible subjects will be included in the analyses.

9.3. Criteria for the termination of the trial.

Subjects participation may be terminated if:

- Allergy occurs after cream application and before tapping of synovial fluid
- Non-compliance to any of the exclusion/inclusion criteria

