11. Quality Control and Quality Assurance

The Quality Assurance department will confirm that the study is conducted in adherence to the protocol for each activity.

In process quality checks and review procedures carried out by the quality assurance department will ensure that the activities and the documentation of the data are done as per the protocol. Deviation from the protocol observed during the quality checks/review will be verified.

12. Ethics

The protocol was reviewed and approved by Temasek Polytechnic IRB. The approval letter is attached in Annex 9.

All the subjects participating in this study will receive full details about the study, the procedures, the risks and the treatment involved by verbal and written form in the Informed Consent Form (Annex 3). Subjects need to sign the Informed Consent Form to confirm their informed agreement to undergo the study.

Remuneration of subjects:

The subjects are already presenting themselves at T&T Family Health Clinic & Surgery for OA treatment.

The subjects who completed the study and agreed to apply the Test product will be adequately compensated. Arthrocentesis cost will be offered free (value \$100 per patient – not per sample).

Patients who do not wish to apply the Test product, but who signed the consent form (i.e Control group) so that their samples can be used for scientific research will be offered a free 45g tube of the Test product.

There is no added inconvenience or impost on them besides the application of a cream on the affected knee. Therefore, the reimbursement is fair and reasonable.

13. Data Handling and Record Keeping

13.1. The holder of the certificate will keep adequate clinical records of each subject for the duration of the clinical trial.

13.2. The holder of the certificate will ensure that such records are:

13.2.1. Kept up to date at all times;

13.2.2. Available at all times for inspection by the licensing authority or any person authorised by him in that behalf; and

13.2.3. Kept at least for whichever of the following periods expires later:

- until there are no pending or contemplated marketing applications of the Test product in Singapore;
 - 2 years after the last approval of a marketing application for the test material in Singapore;
 - where the clinical trial is discontinued, 2 years after the licensing authority has been informed of the discontinuation of the clinical trial under regulation 9;
 - 6 years after the completion of the clinical trial; or

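### Patients choose their own group under different rewards and an unadjusted Z-test compares them, so on this design and analysis alone a positive result cannot be attributed to the cream

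*Combined protocol and SAP*

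**What the plan says.** Section 4.4, on measures against bias, reasons that the analytical results are objective and that randomisation is therefore not needed. On recruitment it says "There is no bias since we take all patients that come in to the clinic for treatment", and on group formation "Patients are not selected for control or test group, they select themselves by choosing (yes or no) to apply the Test product".

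Section 12 attaches a different reward to each choice. For Test, "The subjects who completed the study and agreed to apply the Test product will be adequately compensated", in the form of free arthrocentesis with a stated value of $100 per patient. Patients who decline the cream but consent to the use of their sample "will be offered a free 45g tube of the Test product"; its price is not given.

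The claim to be tested is causal. Section 3.1 proposes that the cream "is able to deliver glucosamine, through the skin, to the synovial fluid of osteoarthritic (OA) joints", and the primary endpoint in section 4.1.1 is "To show that the level of glucosamine in synovial fluid has statistically increased after the Test product topical application". Section 9.1 gives the only planned comparison: "Statistical analysis will be performed using a one-sided Z-test", Test against Control, at P < 0.01, with no covariate named.

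Some safeguards exist:

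- Section 4.9 says "Scientific analysis and testing will be carried out first before revelation of codes".
- Sections 5.2.5 and 5.2.6 exclude patients who took glucosamine or any joint-pain treatment in the previous 24 hours.
- Sections 2.6 and 5.1.3 restrict entry to primary OA and have the OA stage graded on X-ray. The stage is not used in the analysis.
- Section 4.10 allows age and gender as optional sub-group variables, not for adjustment.

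**The concern.** Section 4.4 answers a different question from the one that matters. An objective assay, and testing before codes are revealed, protect the measurement. They do nothing to make the people in the two groups alike. Taking every clinic patient concerns who enters the trial, not how those who enter are divided.

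The division is left to the patient, and the reward differs with the choice. Those who take the cream may differ from those who decline in age, sex, OA stage or glucosamine use before the 24-hour window. If any such factor is also related to synovial glucosamine, the groups differ before any cream is applied.

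The text describes no pre-application sample. Section 4.6 has a single session with the tap after application, and section 2.3 says the trial adds no invasive step. The claim of an increase after application therefore rests entirely on the difference between choosers and decliners. Any prior difference is added to, or subtracted from, the apparent cream effect, and the planned analysis cannot separate the two. A strict significance level limits chance findings, not this bias.

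**Working it through.** **The plan's own figure.** Section 9.2 gives 240 patients, 120 per group, with no effect size, SD or power, so the number cannot be reproduced. Inverting the usual formula shows what it can detect.

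**Inputs.** n = 120 per group (section 9.2); one-sided level 0.01 (section 9.1), so the critical value is z = 2.326. Differences are in units of the SD of glucosamine concentration, because the documents give no SD. Equal SDs and one independent value per patient are assumed.

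**Standard error and threshold.**

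- SE = √(2/120) = 0.129 SD
- Observed difference needed for a positive test = 2.326 × 0.129 = 0.30 SD
- Detectable at 80% power: (2.326 + 0.842) × 0.1291 = 0.41 SD
- Detectable at 90% power: (2.326 + 1.282) × 0.1291 = 0.47 SD

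**No cream effect, prior imbalance of d SD.** The chance of a positive test is P(Z > 2.326 − d/0.1291). Every d is an assumption; a positive d means that Test starts higher.

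| Assumed d (SD) | 2.326 − d/0.1291 | Chance of a positive test |
|---|---|---|
| 0 | 2.326 | 1.0% |
| 0.1 | 1.552 | 6.0% |
| 0.2 | 0.777 | 21.8% |
| 0.3 | 0.003 | 49.9% |
| 0.5 | −1.547 | 93.9% |
| −0.1 | 3.101 | 0.1% |
| −0.2 | 3.876 | 0.005% |

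As an example of scale, a factor worth 1 SD of concentration that is 20 percentage points more common in Test gives d = 0.20 × 1 = 0.2 SD.

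**Real effect of 0.466 SD (90% power when balanced), Control starting higher.** Power = P(Z > 2.326 − (0.466 − imbalance)/0.1291).

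| Control starts higher by (SD) | Power |
|---|---|
| 0 | 90% |
| 0.1 | 69% |
| 0.2 | 39% |
| 0.3 | 15% |

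**Effect of sample size.** With d = 0.2 SD and no cream effect, the chance of a positive test is 10.9% at 60 per group, 21.8% at 120 and 44.6% at 240. More patients make the false-positive problem worse, because the SE shrinks and the bias does not.

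**The case against.** The strongest reply is that bias is possible here but not shown. Confounding needs a factor linked both to accepting the cream and to synovial glucosamine, and the documents establish neither link. Two of the most direct candidates, glucosamine and joint-pain treatment in the last 24 hours, are excluded, and everyone has primary OA with an effusion that needs a tap. The imbalances above are invented for illustration. A difference far larger than any plausible imbalance would be hard to explain away by self-selection. The study is also a single-dose bioavailability study that makes no efficacy claim.

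Much of this is fair as a limit. The size and direction of any imbalance are unknown, and a very large difference would be more persuasive. But the plan sets no such threshold: anything above 0.30 SD counts as positive. Nor can it appeal to stable endogenous levels, since establishing that baseline is its own secondary endpoint (section 4.1.2). The exclusions leave age, sex, OA stage and earlier glucosamine use free to differ.

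Three further points deserve mention:

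- The flowchart in section 4.3 and the Data Record Form cannot be seen, so further recorded covariates cannot be ruled out. A pre-application tap is unlikely given sections 2.3 and 4.6, and section 9.1 analyses no change from baseline.
- Section 12 prices the tap per patient rather than per sample, and section 9.4 discards outliers and non-linear results. Either could alter the 0.129 SD standard error. Neither removes the bias.
- Section 4.6 states the interval of 1 to 3 hours before tapping for Test only. Randomisation would not by itself settle that difference; it is a separate, smaller matter.

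**Conclusion.** The concern holds. Section 4.4 is wrong to conclude that there is no bias and no need for randomisation: its argument covers measurement and recruitment, not how the groups are formed. With self-selection, different rewards and an unadjusted test, a positive result cannot be attributed to the cream on this design and analysis alone.

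The conclusion about attribution needs no assumed figures. The size does: if Test starts 0.1 to 0.3 SD higher, the nominal 1% error becomes 6% to 50%; if Control starts higher by the same amounts, 90% power falls to between 69% and 15%. These are what-if values under assumed imbalances, not estimates for this trial. The fault lies in the only primary comparison, and unmeasured differences between choosers and decliners cannot be corrected once the data are collected. It must be fixed before enrolment.

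**What to change.** **Preferred.** Replace section 4.4 with text such as: *Eligible patients who accept either assignment are randomised 1:1 to Test or Control from a concealed list prepared in advance and opened after consent. Both groups receive the same compensation.* Delete the statements that there is no bias and that randomisation is not needed, and bring section 12 into line. Section 4.8, which says there is no comparator arm, should be reconciled with the Control group in sections 2.6 and 9.2.

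This needs a protocol and consent amendment and an allocation list. The 240 patients, the assay and the tap are unchanged. Patients who will not accept either assignment are not enrolled, so more must be approached, recruitment may be slower, and the endogenous baseline will describe a somewhat narrower population. If free arthrocentesis is extended to Control, the cost is at most 120 × $100 = $12,000, less the tubes saved.

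**Fallback, if self-selection is kept.** Make the primary analysis in section 9.1 a regression of glucosamine concentration on group, adjusted only for pre-application variables: age, gender, X-ray OA stage and, if recorded, glucosamine use before the 24-hour window. Do not adjust for aspirated volume, which in Test is measured after application. State the level, sidedness, outcome scale and handling of missing covariates in advance. Reword sections 3.1 and 4.1.1 as a between-group association. The cost is wording, plus recording earlier glucosamine use if the Data Record Form does not already hold it. This reduces measured confounding only and does not support a causal claim.

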6.1. The treatment to be administered

- 6.1.1. Name: Topical Glucosamine cream, Lynk Biotechnologies Pte Ltd, TGC® Transdermal Glucosamine Cream Plus Capsaicin containing 10% w/w Glucosamine Sulphate.2 KCl, presented as a finished product.
- 6.1.2. Manufactured by DynaLynk Pharma Pte Ltd. GMP certified.
- 6.1.3. Dose: A single dose of 2g (containing 200mg of Glucosamine Sulphate. 2KCl) of the Test product will be applied topically on the knee of the subjects (for Test Group only).
- 6.1.4. Dosing schedule: single dose for subjects of the Test group only. Subjects from the Control Group will not receive any treatment.
- 6.1.5. Route / mode(s) of administration: topical application on the affected knee
- 6.1.6. Follow-up – Not applicable

6.2. Medication(s) / treatment(s) permitted (including rescue medication) and not permitted before and/or during the trial.

Please refer to the exclusion criteria in section 5.2. There is no rescue medication needed.

6.3. Procedures for monitoring subject compliance.

There is no need to monitor the patient’s compliance since the Test product (single dose) will be applied by the nurse on the trial site and the extraction of the synovial fluid will be done by the PI.

7. **Assessment of Efficacy**

There is no efficacy being promoted with a single dose application of the Test product. The objective of the study is to assess the bioavailability of the Test product: in the synovial fluid of OA joints.

8. **Assessment of Safety**

Based on the history of usage of the Test product over the last 10 years with over 250,000 tubes sold, the only adverse effect reported by the consumers relates to minor rashes. Less than 10 complaints of this nature have been received over this period. Adverse side effects related to the Test product topical application are extremely rare.

The emergency number to call when required is [name] (T&T FAMILY HEALTH CLINIC & SURGERY) or [name] (Lynk Biotechnologies' main line). Subjects may also contact Temasek Polytechnic IRB for any questions. IRB contact number is: [name]. These contact numbers are given to each subject in the Informed Consent Form.

Adverse events will be recorded in adverse event form or appropriate documents. We will report to Temasek Polytechnic IRB, within 7 calendar days, the occurrence of any serious adverse events, adverse drug reactions and unanticipated episodes that may occur in the course of this research.

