Subjects are free to withdraw at any time, without giving a reason. This will not affect the standard of care they receive.

9.4. Procedure for accounting for missing, unused, and spurious data.

Using glucosamine concentrations ascertained from the standard addition method, the mean absolute deviation method will be used to eliminate outliers. In addition, non-linear results, with $r^2 < 0.95$, will also be discarded. Data from outliers will be excluded from main analysis.

Missing, unused or spurious data: not applicable in this protocol.

9.5. Procedures for reporting any deviation(s) from the original statistical plan (any deviation(s) from the original statistical plan should be described and justified in protocol and/or in the final report, as appropriate).

Any deviation, if any, will be described in the final report.

9.6. The selection of subjects to be included in the analyses (e.g. all randomised subjects, all dosed subjects, all eligible subjects, evaluable subjects).

All subjects that go for treatment and sign consent form will be part of the study. All samples collected will be analysed.

10. Direct Access to Source Data / Documents

For the purpose of ensuring compliance with the Clinical Trial Protocol, Good Clinical Practice and applicable regulatory requirements, the Investigator should permit auditing by or on the behalf of the Sponsor and inspection by applicable regulatory authorities.

The Investigator agrees to allow the auditors/inspectors to have direct access to his/her study records for review, being understood that these personnel are bound by professional secrecy, and as such will not disclose any personal identity or personal medical information.

The Investigator will make every effort to help with the performance of the audits and inspections, giving access to all necessary facilities, data, and documents.

As soon as the Investigator is notified of a future inspection by the authorities, he will inform the Sponsor and authorize the Sponsor to participate in this inspection.

The confidentiality of the data verified and the protection of the patients should be respected during these inspections.

Any result and information arising from the inspections by the regulatory authorities will be immediately communicated by the Investigator to the Sponsor.

The Investigator shall take appropriate measures required by the Sponsor to take corrective actions for all problems found during the audit or inspections.

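### After a session of at most 4 hours the plan excludes follow-up, so later adverse events, and the outcome of a reaction that ends participation, are captured only if the patient reports them

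*Combined protocol and SAP*

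**What the plan says.** Section 4.6 describes participation as "Single session, up to 4 hours, for the cream application and joint's fluid aspiration". For the Test group, "The tapping of synovial fluid should be done between 1 and 3 hours following cream application". The section closes with "No follow-up needed", and 6.1.6 repeats that follow-up does not apply.

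Section 4.7, repeated in 9.3, lists one reaction for which participation may be ended: "Allergy occurs after cream application and before tapping of synovial fluid".

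Section 8 makes the safety commitments:

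- Adverse events go on an adverse event form or other suitable document.
- The IRB is told within 7 calendar days of "the occurrence of any serious adverse events, adverse drug reactions and unanticipated episodes that may occur in the course of this research".
- Unexpected, related serious events go to the regulator "no later than 15 calendar days after first knowledge that the case qualifies for expedited reporting", with shorter limits for fatal or life-threatening cases.
- Every subject receives telephone numbers for the clinic, the sponsor and the IRB through the consent form.
- The investigator must look after patients' safety, with specialist referral where needed.

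Section 9.6 counts every consenting patient who goes for treatment as part of the study and adds "All samples collected will be analysed".

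**The concern.** Sections 4.6 and 6.1.6 do not merely leave follow-up unmentioned; they rule it out. Section 8 assumes that the study will learn of events, including non-serious adverse drug reactions. The available text gives no collection period, no scheduled contact and no rule for following a reaction to its outcome. From discharge onward, detection depends on the patient's initiative.

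The gap matters most for a patient who reacts before the tap. Participation may be ended, but the dose has already been given. The plan does not say whether recording of the reaction continues, or whether fluid drawn at the routine tap still counts as a study sample.

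What is at stake is how a clean safety record may be read. The product's safety case in 2.3, 8 and 14.2 rests on spontaneous consumer complaints. This trial could add solicited data on 120 dosed patients, but it returns to spontaneous reporting once the session ends.

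**Working it through.** The plan gives no figure for safety follow-up, so there is none to reproduce. The check has four parts.

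**1. Observation window.** Inputs from 4.6: session of at most 4 h; tap 1 to 3 h after application. Assumption: the 4 h start at application. Time left after the tap = 4 − tap time.

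- Tap at 1 h: 4 − 1 = at most 3 h.
- Tap at 3 h: 4 − 3 = at most 1 h.

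Any session time used before application shortens both.

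**2. What an absence of events would show.** Input from 2.6 and 9.2: 120 dosed subjects. With zero events, the one-sided 95% upper bound solves (1 − p)^120 = 0.05:

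p = 1 − 0.05^(1/120) = 0.0247, about 2.5%.

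The chance of at least one event is 1 − (1 − p)^120. At assumed true rates, with every event captured:

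| True rate | Chance of at least one event in 120 |
|---|---|
| 0.1% | 11% |
| 1% | 70% |
| 2.5% | 95% |

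These figures need complete capture. If only a fraction c of events reaches the record, the bound applies to c × p, and the bound on the true rate becomes 2.47%/c. The documents give no value for c. As an illustration, c = 1 gives 2.5%, c = 0.5 gives 4.9% and c = 0.25 gives 9.9%. Without planned contact, c is unknown for events after discharge.

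**3. The existing safety figure.** Fewer than 10 complaints for over 250,000 tubes (2.3, 8, 14.2) is below 10/250,000 = 0.004% of tubes. This counts volunteered complaints per tube. It is not a rate per patient, so it cannot be set directly against the 2.5%.

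**4. Passages side by side.**

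- *4.6 and 6.1.6 against 8.* The first two end contact with the session. Section 8 sets no end to recording. Events after discharge can be recorded, but nothing planned looks for them.
- *4.7 and 9.3 against 8.* Participation may end on an allergic reaction. Section 8 provides for care of the patient but does not mention recording the outcome.
- *4.7 and 9.3 against 9.6.* Section 2.3 says the tap is independent of the trial, so fluid may still be drawn from a patient whose participation has ended. Section 9.6 would have it analysed; 4.7 leaves its status unclear.
- *Section 12.* Control subjects are offered a 45 g tube, equal to 45/2 = 22.5 applications of 2 g. No adverse event collection is described for its use.

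**The case against.** The strongest defence is that a single 2 g topical dose needs little follow-up. The only effect that consumers have reported is mild rash with long-term use (2.3). Section 5.2 excludes patients with known relevant allergies, skin sensitivity or abnormal skin at the site. Safety is not an endpoint. This stands in part: the documents do not show that a delayed reaction to one dose is likely, and how much follow-up is enough is a matter of judgement. It does not answer the mismatch between ruling out follow-up and promising to report.

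A second defence is that a passive route exists. This also stands. A reader might infer that later events cannot enter the record, or that nothing would start the reporting clocks. The documents do not support either reading. Subjects hold contact numbers, recording has no stated cut-off, and an event in the session or a patient's call supplies the first knowledge that starts the regulator's clock. What is missing is active detection.

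Third, termination is permissive and the investigator keeps a duty of care, so it would be wrong to say that a reacting patient is abandoned. The gap lies in recording the outcome. Nor is it a fault that 4.7 says nothing of reactions after the tap: it is a discontinuation rule, and little then remains to discontinue.

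Finally, the flowchart, Data Record Form, adverse event form and consent form are not in the material available. They may contain instructions on timing, and the finding is limited to the text that can be read.

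**Conclusion.** The concern holds in a limited form. Post-session capture of adverse events is passive only, by express statement in two places, while section 8 makes reporting commitments that would be better served by planned contact. Later reactions, and outcomes after participation is ended, may be under-recorded. A finding of 0/120 would support an upper bound of about 2.5% only for events seen in the session or volunteered afterwards. The window of at most 1 to 3 h after the tap assumes that the session clock starts at application.

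A reader might also infer that reacting patients' fluid is discarded and that this biases the Test group mean. The documents do not support this. No section says such fluid is discarded, 9.6 points the other way, and nothing links an allergic reaction to the amount of glucosamine reaching the joint. What remains is an ambiguity about which samples count, confined to the Test group and of unknown direction and size.

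This should be changed because the remedy is cheap and the conflicting statements are explicit. The primary test does not depend on it.

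**What to change.** 1. In 4.6 and 6.1.6, replace the statements excluding follow-up with a stated adverse event collection period and one scripted telephone contact per dosed subject after the session, made by clinic staff and recorded on the existing adverse event form. The sponsor sets the timing. The 7-day IRB limit is a reporting deadline and should not double as the observation window; the section 8 clocks should run from first knowledge.
2. Optionally, make the same call to Control subjects who accept the 45 g tube.
3. Reconcile 4.7 and 9.3 with 8 and 9.6. State that ending participation does not end recording of the reaction and its outcome, and state whether fluid drawn at the routine tap is analysed and flagged. The clinical discontinuation rule itself is for the sponsor.
4. In the report, describe any absence of events as covering the stated collection period and method of contact.

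Cost, at an assumed 5 minutes per call: 120 × 5 = 600 minutes, or 10 clinic hours, for dosed subjects; 240 × 5 = 1,200 minutes, or 20 hours, for everyone. No visit or procedure is added. The downside is that participation is no longer strictly one session. Item 3 is wording only.
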